Study Protocol Official Title: Effect of Emotion Mindsets on Emotion Processing: A Multilevel Experimental Investigation NCT Number: 03978871 September 27, 2023

Research Design and Method

163 adolescent girls with a high FEM (≥.75 SD above the mean on a screening¹⁶) completed these procedures in a single session: (1) baseline measures (demographics, puberty, mindsets, self-efficacy); (2) computer lesson (random assignment to group); (3) post-lesson mindsets, self-efficacy; (4) pre-Trier affect; (5) Trier; (6) post-Trier measures; (7) emotional challenge task (ECT), go-nogo, and resting state in the scanner. The selected tasks provide a multi-level, multi-method assessment of emotion processing, including self-reported negative affect (Trier, ECT; Hyp. Set 1c), naturally occurring *in vivo* ER in response to an ecologically valid stressor (Trier; Hyp. Set 1c), use of an explicit ER prompt (ECT; Hyp. Set 1c), neural correlates of reactivity and regulation (ECT, gonogo; Hyp. Set 1a), neural recovery from emotional challenge (resting state; Hyp. Set 1a), and behavioral indexes of cognitive control (go-nogo; Hyp. Set 1b). At 2- and 4-month follow ups, girls completed via the Internet the mindset and self-efficacy measures and a self-report measure of ER in daily life.

Girls completed a 25-minute computer lesson with audio-recordings. The **GEM** manipulation, adapted by our research team from a well-validated mindset manipulation⁶⁵⁻⁶⁸, involves 6 components: (1) Introduction: discussion of emotional experiences in teenagers; (2) Explanation of neuroplasticity, emphasizing the potential for changes in the brain and modification of emotions during adolescence; (3) Scientific evidence for the effect of ER training on mood improvement; (4) Comprehension assessments: brief factual quizzes and written summary of key points; (5) Vignettes and written testimonials: scenarios in which older youth describe challenging situations when they felt negative emotions and used growth mindsets to help regulate their emotions; and (6) Self-persuasion exercise: a. Girls read a hypothetical scenario about an emotional challenge and describe their likely thoughts and feelings; b. Girls imagine the same event happening to another (younger) teen and help them understand how they can change, integrating what they learned about malleability of the brain and emotion. The **CONT** condition involves a structurally similar session, with the same number and type of reading and writing activities, that focuses on general education about the brain⁷⁴.

Manipulation check. Before and after the lesson and at the follow-ups, girls completed a measure of mindsets about emotion, adapted from Tamir¹⁶ to focus on teens (e.g., "The truth is, teens have very little control over their emotions."). The original measure has well-established psychometrics and is distinct from mindsets about other personal attributes¹⁶. Pilot data support the validity of the revised measure and support a single emotion mindset factor, $\chi^2(47) = 125.82$, CFI = .97, SRMR = .032.

Self-efficacy. Before and after the lesson and at the follow-ups, girls completed measures of ER self-efficacy¹⁶.

Social stressor. Using an adapted version of the Trier Social Stressor Test¹⁰⁴⁻¹⁰⁶, girls prepared a speech in which they convince a group of peers (who ostensibly will watch a video of the speech; in reality, there are no peers) that they should be selected for a fictional TV show about teens' ability to form friendships. Girls faced a computer screen displaying their image while preparing (1 min.) and presenting (3 min.) a speech. A female "evaluator" entered the room with a clipboard prior to the speech and fixed her gaze on the screen, avoiding eye contact. At intervals of 20 sec., she marked the clipboard. This task is well-validated for eliciting meaningful variability in adolescents' emotion reactivity and ER¹⁰⁴⁻¹⁰⁶. Before and after the Trier, girls rated several dimensions of state negative affect⁵². **Emotion reactivity** was reflected in a residualized score. After the Trier, girls rated their use of *in vivo* **ER strategies**: cognitive reappraisal (e.g., "I tried to think about the speech in a way that made me feel better."), positive thinking (e.g., "I imagined myself doing a great job on the speech."), rumination (e.g., "I kept thinking about how stressed I felt."), avoidance (e.g., "I tried not to think about how I felt."), and helplessness (e.g., "I felt there was nothing I could do to stop feeling stressed.")^{54,57-59}. Girls then underwent scanner training.

Scan procedures. The scan consisted of **4 segments**: (1) neutral video; (2) emotional challenge task (**ECT**); (3) 8 min. resting state; and (4) emotional go-nogo task.

• ECT. Girls watched validated videos created for fMRI¹⁰⁷⁻¹⁰⁸ depicting females making one of three types of statements with matching affective expression: negative (criticism; e.g., "You are a disappointment."), positive (praise; e.g., "You will be successful."), or neutral (e.g., "Pools have chlorine."). Before each video, girls received a prompt (2 sec.) instructing them to imagine how they would feel if the female were a friend speaking to them ("YOU"; **immerse**), or an actor practicing her lines ("ACTOR"; **reframe**). These cues make the statement either more (immerse) or less (reframe) personally relevant, with the reframe cue providing a proactive ER strategy. After the cue, there was a pause (2-7 sec.), presentation of the video (6 sec.), and another pause (3 sec.). After each trial, the participant rated how bad she felt on a 5-point scale. Comparing brain activation and negative affect during the criticism vs. neutral videos in the immerse trials provides an

index of **emotion reactivity**¹⁰⁷⁻¹⁰⁸. Comparing brain activation and negative affect during the criticism videos in the reframe vs. immerse trials provides an index of **ER success**¹⁰⁷⁻¹⁰⁸.

- **Resting state**. Girls fixated on a central cross. The resting state captured residual effects of ER efforts imposed during the immediately preceding ECT. Greater ability to flexibly engage and disengage ER in response to changing external challenges (imposed by negative, positive, and neutral videos) is expected to be reflected in the functional connectome for minutes beyond the ECT, as reflected in more within-network connectivity in cognitive control (CC) networks as well as more between-network connectivity with the AMY in girls who engage in proactive ER.
- Emotional go-nogo. Girls completed a CC task with emotion distractors¹⁰⁹ depicting negative (social rejection), positive (social acceptance), or neutral (scrambled) images¹¹⁰. Letters were presented sequentially at the center of the screen, with distractors in the background. The distractors were presented alone (350ms), prior to the letter (750ms), to make them difficult to ignore. Girls were instructed to ignore the images and respond as quickly as possible without sacrificing accuracy with a button press to every letter (go trials), except for Xs (no-go; 25% of trials). Girls acquire a prepotent tendency to press and must inhibit their responses during X trials. Research supports the validity of emotional go-nogo tasks¹⁰⁹⁻¹¹¹. Reaction time (RT) and accuracy scores provide an index of ER.

2- and 4-month follow-ups. Youth completed the mindset measure, self-efficacy measures, and a measure to assess ER (e.g., cognitive reappraisal, rumination) in daily life. Items were drawn from existing measures¹¹²⁻¹¹⁷ or written for this measure. Pilot data in 158 adolescents support links between emotion mindsets and these self-reports of ER.

The fMRI data were collected using a Siemens Prisma MRI 3 Tesla scanner. A standard 64-channel (phased array/transmit-receive) birdcage coil was used to collect imaging data. Sessions began with a Siemens Autoalign routine, with subsequent manual realignment when needed to ensure the dorsal portion of the participant's brain was within the acquisition volume. This was followed by an anatomical scan, a shimming routine to optimize signal-to-noise ratios, opposite-phase-encoded field maps, the social evaluation task, resting-state scan, and ended with the socioemotional go/no-go task. The highresolution anatomical scan consisted of a 3D sagittal acquisition of T1-weighted magnetizationprepared rapid-acquisition gradient echo (MPRAGE) sequence (TR = 2300 ms; TE = 2.32 ms; TI = 950 ms; 8° flip angle; bandwidth = 200 Hz/Px; GRAPPA factor = 2; in-plane matrix = 256 × 256; FOV = 240 mm × 240 mm; slice thickness = 0.9 mm; 192 slices). Both tasks and the resting-state scan employed similar CCMR multiband T2*-weighted echoplanar imaging (EPI) protocols (TR = 1020 ms; TE = 30 ms; 52° flip angle; bandwidth = 2272 Hz/Px; MB factor = 3; GRAPPA factor = 2; matrix = 88 × 88; FOV = 220 mm × 220 mm; slice thickness = 2.25 mm; slice gap = 0.225 mm; 51 slices), varying in volumes collected for the SET-II (830 volumes), resting-state (480 volumes), and Emotional Go/No-Go (580 volumes) scans. The use of Center for Magnetic Resonance Research (CMRR) multiband sequences enables the acquisition of BOLD images with superior temporal resolution compared to traditional single band protocols while maintaining an acceptable signal-to-noise ratio (Feinberg et al., 2010; Xu et al., 2013).

## **Statistical Design and Power**

Originally planned sample size: 150

Final sample size: 163 (due to scan problems in 13 participants)

**Power**. Power for ANCOVAs and MANCOVAs was calculated with  $G^*$ Power. Based on prior research, we expect a large effect size for the mindset manipulation and medium or medium-to-large effects on emotion processing (e.g., medium to large effects, including for Group x Time interactions, were found for biological stress responses). With N = 150, power to detect a medium or large manipulation effect (Group x Time interaction) is >.99. Power to detect a medium univariate or multivariate group effect is >.86. Power to detect a medium univariate or multivariate Group x Time interaction is >.99. Power to detect a medium indirect effect using Monte Carlo simulations in Mplus is >.99.

**MRI** data. MRI data were preprocessed with fMRIPrep v21.0.0 (Esteban et al., 2018; Esteban et al., 2020; RRID:SCR\_016216), a Nipype v1.6.1-based tool (Gorgolewski et al., 2011; Gorgolewski et al., 2018; RRID:SCR\_002502). All preprocessing was implemented via an internal HPC image processing pipeline hosted by the Beckman Institute for Advanced Technology (v0.5.0 https://pipeline-hpc.readthedocs.io/).

A fieldmap of B0-non-uniformity was estimated from two EPI reference images using the TOPUP method (Andersson, Skare, and Ashburner (2003); FSL 6.0.5.1:57b01774). T1-weighted (T1w) volumes were corrected for intensity non-uniformity using this fieldmap via N4BiasFieldCorrection v2.1.0 (Tustison et al., 2010) from ANTs v2.3.3 (Avants et al. 2008, RRID:SCR\_004757). These were used as T1w references throughout the workflow—and skull-stripped using antsBrainExtraction.sh v2.3.3 (using the OASIS30ANTs template). Brain tissue segmentation of cerebrospinal fluid (CSF) and white-matter (WM) were performed on the brain-extracted T1w using the FAST routine from FSL (FSL 6.0.5.1:57b01774, RRID:SCR\_002823, Zhang, Brady, and Smith 2001). Spatial normalization to the MNI152NLin6Asym template (Evans et al. (2012), RRID:SCR\_002823; TemplateFlow ID: MNI152NLin6Asym) was performed through nonlinear registration with the antsRegistration tool (ANTs v2.3.3) using brain-extracted versions of both T1w volume and template.

For each BOLD run, a reference volume and its skull-stripped version were generated from a spatially aligned single-band reference image. Head-motion parameters with respect to this reference were then estimated using MCFLIRT (FSL 6.0.5.1:57b01774, Jenkinson et al. 2002). Slice-timing correction to 0.47s was performed using 3dTshift from AFNI (Cox and Hyde 1997, RRID:SCR\_005927). The BOLD reference was then co-registered to the T1w reference using bbregister (FreeSurfer; Greve and Fischl, 2009) employing 6 degrees of freedom.

Additional confounding time-series were calculated for later nuisance regression based on the preprocessed BOLD. These included Powers et al. (2014) and Jenkinson et al. (2002) framewise displacements (FD), and global signals computed from application of CSF and WM masks. Volumes exhibiting greater than 5mm of framewise displacement were marked for scrubbing.

All resampling was performed with a single interpolation step by composing all the pertinent transformations (i.e., susceptibility distortion correction, head-motion realignment, and co-registrations to anatomical space). Gridded (volumetric) resamplings were performed using antsApplyTransforms (ANTs), configured with Lanczos interpolation to minimize smoothing effects. Results were visually inspected to verify successful preprocessing and identify images with significant signal dropout or other artifacts warranting exclusion from analysis. Preprocessed BOLD runs were subsequently smoothed using a 6mm FWHM Gaussian kernel implemented through SPM12 (Ashburner et al., 2014).

Linear contrasts for each planned comparison were created for each participant. BOLD signals were averaged across voxels within each ROI. We used Monte-Carlo simulations using the 3dClustSim tool in AFNI (Cox et al., 2016) to determine the minimum cluster size for the relevant contrasts at the whole-brain level (pvoxel-level < .005, pcluster-level < .05). CC ROIs were defined via reference to a functional atlas with adjunctive anatomical labelling (Schaeffer et al. (2018) 400 parcel, Yeo 7-network, FSLMNI152, 1mm resolution atlas). ROIs were constructed by aggregating spatially contiguous ROIs belonging to both the same anatomical region and same Yeo-7 network membership into single larger ROIs. This resulted in 27 ROIs assigned to the cingulo-opercular network (CON) and frontal-parietal network (FPN). Left and right AMY ROIs were defined via reference to the AAL1.V4 atlas (Tzourio-Mazover et al., 2002). **Neural reactivity** scores reflect activation in the AMY (activation

in the CON also will be explored given its potential role in both emotion reactivity and regulation). For resting state, neural regulation scores will be calculated by: (1) constructing connectivity matrices consisting of pairwise Pearson's correlations across ROIs in the FPN and CON; and (2) creating aggregate scores by averaging correlations for each CC network of interest (FPN-AMY, CON-AMY), separately for each contrast of interest. For functional tasks, psychophysiological interaction analyses will be conducted.

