## **Planned Analyses**

Manipulation check (Teen Emotion Mindset Measure): A Group (GEM, CONT) X Time (pre-manipulation, post-manipulation) ANCOVA will be conducted to test whether the mindset manipulation changes girls' mindsets about the malleability of emotion. It is expected that the GEM but not CONT group will show increases in their growth mindsets following the manipulation (Group X Time interaction). Similar analyses will be conducted for the 2- and 4-month follow-up mindset measures. The interaction here and in the following analyses will be decomposed by conducting paired comparisons within group. All analyses will adjust for relevant covariates.

**Hypothesis Set 1a (Brain activation):** Whole-brain and ROI analyses (MANCOVAs) will examine whether the GEM group relative to the CONT group shows (a) lower activation in the AMY contrasting the criticism vs. neutral videos in the immerse trials of the ECT, and the negative vs. neutral distractors in the go-nogo task (i.e., less **emotion reactivity**); and (b) stronger intrinsic and task-related connectivity between the AMY and the CC networks of interest (FPN and CON) contrasting the criticism videos in the reframe vs. immerse trials of the ECT, negative vs. neutral distractors in the go-nogo task, and during resting state (i.e., stronger **ER**).

**Hypothesis Set 1b (Behavioral modulation of emotion):** Analyses will examine whether a GEM predicts better behavioral modulation (attentional control) of emotion. A MANCOVA will be conducted to test whether the GEM relative to the CONT group is better able to ignore negative emotion (vs. neutral) distractors, resulting in faster RTs and better accuracy.

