Hypothesis Set 1c (state negative affect, Emotion Regulation Strategies, Emotional Self-Efficacy Scale): To examine emotion reactivity, Group (GEM, CONT) X Time or Group X Trial ANCOVAs will be conducted to test whether the GEM relative to the CONT group reports less of an increase in negative affect (across the Trier) and less negative affect after the criticism vs. neutral videos in the immerse trials (ECT). To examine ER success, Group X Trial ANCOVAs will be conducted to test whether the GEM relative to the CONT group reports less negative affect after the criticism reframe vs. immerse trials (ECT). To examine ER strategies, a MANCOVA will be conducted to test whether the GEM relative to the CONT group reports using more proactive *in vivo* strategies during the Trier. To examine long-term effects on ER strategies, a similar MANCOVA will be conducted using the 2- and 4-month follow-up data on self-reported ER. To examine self-efficacy, a Group (GEM, CONT) X Time (pre-manipulation, post-manipulation) ANCOVA will be conducted to test whether the GEM relative to the CONT group shows bigger increases in self-efficacy.

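### Is the stated power above .99 for a medium Group x Time interaction inconsistent with the .86 given for a medium group effect?

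*SAP*

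**What the plan says.** The SAP, Statistical Design and Power, names G*Power and an originally planned sample of 150. It gives three power statements that bear on this point:

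- Manipulation effect: "With N = 150, power to detect a medium or large manipulation effect (Group x Time interaction) is >.99".
- Group effect: "Power to detect a medium univariate or multivariate group effect is >.86".
- Interaction on the emotion-processing outcomes: "Power to detect a medium univariate or multivariate Group x Time interaction is >.99".

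Effect sizes appear only as verbal labels. The paragraph gives no f or d, alpha, correlation between occasions or effect-size option. It expects a large effect for the manipulation and medium or somewhat larger effects on emotion processing.

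Planned Analyses then uses the interaction tests. In Hypothesis Set 1c, "Group (GEM, CONT) X Time or Group X Trial ANCOVAs will be conducted" for negative affect across the Trier and in the ECT, and a Group x Time ANCOVA is planned for self-efficacy. The section also says "All analyses will adjust for relevant covariates", without naming the covariates or the variance they should explain.

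**The concern.** Two adjacent sentences use the word medium, and the reported miss rate falls from about 14% to under 1% between them. With two groups and two occasions (or two trial types), the interaction test is exactly a two-sample test on each girl's difference score. If medium means d = .5 on that score, its power equals that of the group effect, about .86.

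What is at stake is the reading of null results. The interaction tests carry Trier reactivity, ECT negative affect, regulation success and self-efficacy. A reader who takes .99 at face value would treat a null interaction as nearly ruling out a medium effect. If the effect in mind were d = .5 on the difference score, that inference would be too strong.

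**Working it through.** **Inputs.** From the SAP: N = 150, two groups, two occasions, the label medium. Assumed, because the power paragraph does not give them: alpha .05 two-sided, 1:1 allocation, and f = .25 (d = .5) for medium. The correlation between occasions, rho, is varied. Power comes from the noncentral F distribution with noncentrality λ.

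**1. Group effect.** λ = N f² = 150 × .0625 = 9.375, df 1 and 148. Power = .860. The SAP's figure reproduces.

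**2. Interaction, repeated-measures convention.** λ = N m f² / (1 − rho) with m = 2 occasions, so λ = 18.75 / (1 − rho).

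| rho | λ | Power |
|---|---|---|
| 0 | 18.75 | .990 |
| .3 | 26.79 | .9993 |
| .5 | 37.50 | .99998 |

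The SAP's figure reproduces from the same f, and a positive rho only raises it.

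**3. What f = .25 means in each case.** For two groups, f = d/2, so the group effect is .5 SD. In a 2 × 2 interaction the cell effects are ± D/4, where D is the between-group difference in change in raw SDs. So f = D/4, and f = .25 gives D = 1.0. Partial eta-squared is λ/(λ + N):

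- group effect: 9.375/159.375 = .059
- interaction at rho 0: 18.75/168.75 = .11
- interaction at rho .5: 37.5/187.5 = .20

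**4. The same size on other scales, N = 150.**

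- d = .5 on the difference score: λ = 9.375, power .860.
- D = .5 raw SD, analysed as a change score: λ = 4.6875 / (1 − rho).
- D = .5 raw SD, adjusted for a baseline: λ = 9.375 / (1 − rho²), df 1 and 147.

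| rho | Change score | Baseline-adjusted |
|---|---|---|
| 0 | .576 | .860 |
| .3 | .729 | .890 |
| .5 | .860 | .940 |
| .7 | .975 | .989 |
| .75 | .990 | .996 |
| .8 | .998 | .999 |

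A .5 raw-SD effect therefore also reaches .99, at rho of about .75 (change score) or .705 (baseline-adjusted). For d = .5 on the difference score, covariates would have to explain about half its variance: 9.375/(1 − .5) = 18.75, the λ that gave .990 in step 2.

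**5. Which column fits which outcome.** Self-efficacy has a measure before the lesson, so the baseline-adjusted column fits. ECT ratings are made in the scanner after the lesson ("After each trial, the participant rated how bad she felt on a 5-point scale"), so the change-score column fits. The protocol says Trier reactivity "was reflected in a residualized score", but its Research Design and Method section puts the pre-Trier rating after the lesson. The lesson may already have moved that rating, so the baseline-adjusted column cannot be assumed for it.

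**6. Manipulation check.** The SAP expects a large effect here. At d = .8 on the difference score, power is .998, so the claim above .99 stands for the expected effect on that scale.

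**7. Limit.** The multivariate claims are not tested here, because the power paragraph gives neither the number of outcomes nor a multivariate effect size.

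**The case for a change.** The best case for a change is that one word covers two effects that differ twofold in raw SD units, with no sign of this to the reader. Putting the interaction on the difference-score scale at d = .5 lowers power from above .99 to .86. For the ECT tests, which have no pre-lesson baseline, a .5 raw-SD difference would be missed 27% of the time at rho .3 and 2.5% at rho .7. Stating the inputs would cost only a few words.

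The missing inputs are a fair observation, and so is the twofold difference on the inferred reading. Three things do not follow from it:

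- **The .99 is not shown to be wrong.** It reproduces under a standard convention at any rho from 0 upward. The .86 depends equally on unstated inputs: f, alpha and allocation.
- **The lower figures are conditional.** Each rests on a scale or a rho that the documents do not supply. On the raw scale, power for a .5 SD effect runs from .58 to .998 for change scores as rho goes from 0 to .8. The SAP never says that medium is the same raw effect for a group comparison and for an interaction.
- **Nothing downstream moves.** The .99 could stay once labelled with its convention, so even full agreement would leave the tests and the sample as they are.

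**Conclusion.** The concern does not call for a change. Both univariate power figures reproduce at N = 150 from f = .25: .860 for the group effect and at least .990 for the interaction. This assumes alpha .05, 1:1 allocation and the repeated-measures convention, an inferred reading because the power paragraph does not name the option.

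What remains is missing detail and a debatable choice of scale. On the inferred reading, the interaction figure is power for a 1.0 raw-SD between-group difference in change, twice the .5 SD behind the group figure. Anyone interpreting a null interaction should keep that in mind and rely on the confidence interval for the effect, not on the planning power.

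The protocol describes data collection as complete, with 163 girls. At that size, d = .5 on the difference score has power .887. A .5 raw-SD effect adjusted for a true baseline has .914 to .993 for rho from .3 to .7, if all 163 contribute. Writing down the inputs now would improve the record but would change no sample size, test or result.

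### The only numeric motion rule in the SAP, a 5 mm framewise-displacement cut on an unnamed measure, leaves jumps of almost two voxels unmarked and must be confirmed or corrected

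*SAP*

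**What the plan says.** The rule is in the SAP, Statistical Design and Power, in the paragraphs on MRI data: "Volumes exhibiting greater than 5mm of framewise displacement were marked for scrubbing". The sentence just before it lists two types of "framewise displacements (FD), and global signals computed from application of CSF and WM masks". The scrubbing sentence names neither type.

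The same paragraphs describe three other protections:

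- **Realignment:** "Head-motion parameters with respect to this reference were then estimated using MCFLIRT".
- **Nuisance regression:** "Additional confounding time-series were calculated for later nuisance regression based on the preprocessed BOLD". The final set of regressors is not listed. The first word of that sentence suggests that the motion parameters may be used as well.
- **Visual inspection:** a check of the preprocessed results, partly to "identify images with significant signal dropout or other artifacts warranting exclusion from analysis".

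The SAP's Planned Analyses add that all analyses adjust for relevant covariates, which are not named.

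The protocol's acquisition paragraph gives the EPI geometry, "matrix = 88 × 88; FOV = 220 mm × 220 mm; slice thickness = 2.25 mm; slice gap = 0.225 mm", and a repetition time of 1020 ms. The functional runs have 830, 480 and 580 volumes, so the rule governs 830 + 480 + 580 = 1,890 volumes per girl.

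**The concern.** A scrubbing threshold is meant to remove volumes in which the head moved enough to corrupt the signal. A cut of twice the voxel width does little of that work, because only extreme jumps exceed it. Since the SAP computes two FD measures and ties the cut to neither, the rule also cannot be reproduced from the text.

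The outcomes at stake are those of Hypothesis Set 1a: amygdala activation, task-based psychophysiological interactions and resting-state Pearson correlations. All are computed from the volumes that remain. Motion artefact left in them adds noise and makes a group difference harder to detect. Hypothesis Sets 1b and 1c rest on behaviour and self-report and do not use these volumes.

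**Working it through.** **The plan's figure.** The 5 mm cut is stated without inputs or derivation, so it cannot be reproduced. It can only be compared with the trial's own image geometry.

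**Inputs (protocol, acquisition paragraph).** Field of view 220 mm, matrix 88, slice thickness 2.25 mm, slice gap 0.225 mm, repetition time 1.02 s.

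**Step 1: the cut in voxels.**

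- In-plane voxel = field of view / matrix = 220/88 = 2.5 mm.
- Slice pitch = thickness + gap = 2.25 + 0.225 = 2.475 mm.
- Cut / in-plane voxel = 5/2.5 = 2.00.
- Cut / slice pitch = 5/2.475 = 2.02.

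The rule therefore acts only on displacements above about two voxels between volumes 1.02 s apart, if the movement is along one axis.

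**Step 2: what each measure leaves unmarked.** The documents cite the two FD measures but do not define them. I assume:

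- (a) Sum type: the sum of absolute translations, plus rotations in radians multiplied by 50 mm.
- (b) RMS type: √[(2/5)·R²·Σ(rotation²) + Σ(translation²)], with R = 80 mm.

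| Movement between volumes | Sum type (mm) | RMS type (mm) | Marked at > 5 mm? |
|---|---|---|---|
| 2.5 mm on one axis (one voxel) | 2.50 | 2.50 | neither |
| 4.9 mm on one axis (4.9/2.5 = 1.96 voxels) | 4.90 | 4.90 | neither |
| 5° rotation about one axis | 4.36 | 4.42 | neither |
| 1.6 mm on each of three axes | 4.80 | 2.77 | neither |
| 2.8 mm on each of three axes | 8.40 | 4.85 | sum type only |

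For example, 5° = 0.0873 rad gives 50 × 0.0873 = 4.36 for the sum type and √(0.4 × 6400 × 0.0873²) = 4.42 for the RMS type. The translation rows do not depend on the assumed radii.

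**Step 3: how much the choice of measure matters.** For equal translations on three axes, the sum type reaches 5 mm at 5/3 = 1.67 mm per axis. The RMS type reaches it at 5/√3 = 2.89 mm per axis. Movements between these values are marked under one measure and not under the other.

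**Step 4: could 5 be a misprint?** The SAP writes its voxel and cluster p-values without a leading zero (.005, .05), so a decimal point could have been lost before the 5. But it gives the slice-timing target as 0.47 s, and the protocol gives the slice gap as 0.225 mm, both with a leading zero. The typography does not settle the matter.

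**The case against.** Four points can be made for the plan.

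**Other safeguards exist.** The data are realigned, regressed on nuisance series, smoothed at 6 mm and visually inspected. This stands in part. These steps may reduce motion effects, and inspection may exclude some bad images. So the text shows that such volumes are not marked by this rule, not that every one of them reached the analysis. But none of these steps sets a numeric motion limit in the text available. One part of the SAP was not available, so a run-level rule there cannot be ruled out. Such a rule would still leave the 5 mm sentence, and its unnamed measure, as it is.

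**On the sum measure the cut can be less loose.** Spread equally over six parameters, 5 mm is 5/6 = 0.83 mm on each, which is below a voxel. This is correct for diffuse movement. It does not help for a jump along one axis, where both measures give the displacement itself.

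**Assignment was random.** A reader might infer that loose scrubbing biases the group comparison. The documents do not support that. The protocol assigns the lesson at random, so habitual differences in motion are balanced in expectation. Bias would need the lesson, given earlier in the same session, to change movement in the scanner, and nothing in the documents shows this.

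**It may be a typing error.** It may be, and the point does not depend on the answer. A misprint in the only stated numeric motion rule still needs correcting.

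**Conclusion.** The point holds as a request to confirm or correct a threshold, and it should be acted on. As written, the rule leaves single-axis jumps of up to almost two voxels unmarked under either FD measure. It also does not say which measure decides the multi-axis cases. The one-axis result needs only the protocol's geometry and the premise that either measure equals the displacement for a pure one-axis shift. The rotation row needs the assumed radii.

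The consequence, if 5 mm was applied, is added noise in the Hypothesis Set 1a outcomes. The documents give no FD distribution and no count of scrubbed volumes, so the size of the effect is unknown. Two stronger conclusions are not supported: that the imaging comparison is biased in favour of either group, and that the intended cut was a particular smaller number. Confidence is medium, mainly because a misprint cannot be excluded.

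**What to change.** 1. Check the analysis scripts. State in the SAP the threshold that was used and the FD measure to which it applied.
2. If 5 mm is a misprint, correct the figure. No re-analysis is needed, and the cost is one sentence.
3. If 5 mm was applied, re-run the first-level models and connectivity analyses on the existing data. Use a threshold that is a small fraction of the 2.5 mm voxel on the named measure, fixed without sight of study arm. Label it a post hoc sensitivity analysis and report it beside the 5 mm results, with FD and the number of scrubbed volumes by arm. The by-arm figures would also show whether motion differed between the groups.

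The third step needs computing and reporting time but no new data. Its downside is that some volumes are lost and two sets of results must be presented.
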